Appendix 1 New elderly hip fracture anesthesia strategy

	The measurement of anesthesia	Implementation	Explanation
Preoperative management	是否 48 h 内实施手术 Surgery within 48 hours?		2 points: <48h, 1 point: <72h>48h, 0 point: >72h.
	Complete analgesia (12 hours in admission), VAS<4 points		2 points: <12h , 1 point: <24h and >12h, 0 point :>24h.
	Preoperative transfusion Hb<80~90 g/L, Patients with ischemic heart disease preoperative transfusion Hb<100 g/L.		2 points: complete comply, 1 point: partly comply, 0 point: not follow
	Uptaking oxygen within 12 hours after injury, according to blood oxygen status to determine whether to continue to absorb oxygen after 12 hours. Target of SpO2 is 92% ~ 98%. Coexisting chronic respiratory disease or II respiratory failure patients should maintain SpO2 in 88% ~ 92%		2 points: complete comply, 1 point: partly comply, 0 point: not follow
	Arrange the degree of doctor in vice director or above		2 points: complete comply, 0 point: not follow
Management during operation	Regional block technology analgesia		2 points: complete comply, 0 point: not follow
	Insulation measure		2 points: complete comply, 1 point: partly comply, 0 point: not follow
	Temperature monitoring		2 points: complete comply, 0 point: not follow
	Arterial Blood Pressure		2 points: complete comply, 0 point: not follow
	Preoperative, intraoperative and		2 points: complete comply, 1 point:

	postoperative blood volume optimization measures		partly comply, 0 point: not follow
术后管理	Maintain Hb no lower than 90 g/L		1 point: partly comply, 0 point: not follow
	Oxygen therapy lasts at least 24 hours, patients with hypoxemia continuously inhaling oxygen		2 points: complete comply, 1 point: partly comply, 0 point: not follow
	Postoperative analgesia		2 points : Nerve block analgesic technique, 1 point : Epidural analgesia, 0 point: Only vein or oral or no analgesia

Note: 2 points: completely comply with the specified implementation as required (the desired index), 1 point: partly compliance (partly implemented, lack of time or (take measures not exceeding the expectation index), 0 point: did not comply with the corresponding measures (no measurement implemented).

Investigator declaration

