(1). New “guideline” anesthesia strategy team (Group A)

(2). Current anesthesia strategy team (Group B)

6. Primary outcome

Mortality of postoperative of 6 months.

7. Secondary outcomes

(1). The intensity of postoperative pain using Visual Analogue Scale (VAS) – collected within two days after surgery

(2). The incidence of postoperative complications – collected post-operation to discharge

(3). Mortality for postoperative of 30 days and 1 year – collected within 30 days and 1 year after surgery

(4). Length of time after surgery to death

(5). The level of compliance of new “guideline”(from the ratio of score: total score) – duration of hospital stay, an average of 2 weeks

(6). Length of hospital stay – up to discharge, an average of 2 weeks

(7). Total cost in hospital and expenditure for anesthesia – length of hospital stay, an average of 2 weeks

(8). Cognitive function with Mini-Mental State Examination (MMSE) – within two days after surgery

(9). Overall satisfaction of patients - collected no more than two weeks before discharge

8. Study withdrawal

(1) Subject can withdraw from the study at any time without giving any explanation, and will not

lose the right to medical care in the future;

(2) The primary orthopedic physician or anesthesiologist believes that the patient's condition is

not suitable for continuing the study;

(3) During the study, if two anesthesia management strategies were found significantly different

in prognosis of patients and could be terminated in advance;

(4) The ethics committee demands that the study be terminated.

9. Implementation of anesthesia strategies and data collection

Three anesthesiologists were assigned to adopt the new "guideline" of the anesthetic strategy, and

the anesthesia management of group A was carried out. Other anesthesiologists performed the

management of group B in accordance with their own routine. A research nurse was assigned to

collect data from preoperative and operative procedures and to complete random grouping. Another

study nurse (who was blind of grouping condition) was assigned to collect the postoperative data to

[figure not shown]
avoid subjective bias and to blind the observer. The data collection table is table 1 below.

Table1: data collection

Period	Variable	Approach
Preoperative data	Age, gender, address, type of fracture, past medical history, ASA grade, cognitive function(MMSE), POSSUM grade, VAS grade	Medical history, MMSE, visit

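### The postoperative haemoglobin row of Appendix 1 has no full-compliance score, which contradicts the Note and leaves the compliance total at 25 or 26

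*Protocol*

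**What the plan says.** Protocol section 7, item (5), defines compliance with the new guideline as a ratio: "from the ratio of score: total score". No numeric total is given there, in the study summary or in Appendix 1.

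Appendix 1 lists 13 items: five preoperative, five intraoperative and three postoperative. Each row prints its own scoring levels. For the postoperative item "Maintain Hb no lower than 90 g/L" the levels are "1 point: partly comply, 0 point: not follow", with nothing above 1. The other 12 rows all include a 2-point level.

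The Note under the table sets the general scale. Its top level is "2 points: completely comply with the specified implementation as required (the desired index", and no item is excepted. Its middle level is "1 point: partly compliance (partly implemented, lack of time or (take measures not exceeding the expectation index".

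The preoperative oxygen item begins "Uptaking oxygen within 12 hours after injury", so its clock starts at injury. The preoperative analgesia item in the same block starts its 12-hour clock at admission. The entry criteria in section 4 set no limit on time since injury, and Table 1 in section 9 lists neither time of injury nor time of admission.

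**The concern.** The row and the Note give different answers for a patient whose haemoglobin meets the target throughout. The row offers only the partial or the failed level; the Note offers 2 points. Two scorers following the same appendix could enter different numbers for the same care, and two analysts could divide by different totals.

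The ratio is a named secondary outcome. It also answers objective 2 (how far current practice complies with the guideline) and feeds the between-group compliance analysis in section 17(3), which is the trial's evidence on how much of the bundle each group received. An item that cannot separate full from partial compliance does that job less well, and a ratio without a fixed denominator has no unique value.

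**Working it through.** The protocol states no total score and no target ratio, so there is no figure of its own to reproduce. The check is a count of Appendix 1.

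**Maximum score**
- Items: 5 + 5 + 3 = 13.
- By the printed rows: 12 × 2 + 1 = 25.
- By the Note: 13 × 2 = 26.

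**Ratio for a patient with full marks on the other 12 items (12 × 2 = 24 points)**

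| Rule applied | Haemoglobin fully met | Haemoglobin partly met |
|---|---|---|
| Rows for score and total | (24 + 1)/25 = 1.000 | (24 + 1)/25 = 1.000 |
| Note for score and total | (24 + 2)/26 = 1.000 | (24 + 1)/26 = 0.962 |
| Row for score, Note for total | (24 + 1)/26 = 0.962 | (24 + 1)/26 = 0.962 |

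Under the rows, and under the mixed rule, full and partial compliance on this item cannot be told apart. Only the Note separates them. The opposite mixture, with the Note for the score and the rows for the total, gives 26/25 = 1.04, which is not a possible ratio. The two rules therefore cannot be used together.

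**Size**
- With the total held at 26, capping the row at 1 costs each fully compliant patient 1/26 = 0.038.
- The shift in the difference between group means is (pA − pB)/26, where pA and pB are the proportions fully compliant on this item. The protocol gives neither proportion. Its absolute value lies between 0 (equal proportions) and 0.038 (proportions differing by 1).

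**Oxygen item, assuming the haemoglobin row is repaired and the total is 26**

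For a patient admitted more than 12 hours after injury who receives everything else:
- oxygen scored 1: (24 + 1)/26 = 0.962;
- oxygen scored 0: 24/26 = 0.923;
- oxygen scored 2, if the parts of the item that still apply are taken as full compliance: 26/26 = 1.000.

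Appendix 1 does not say which applies. The protocol does not give the share of such patients.

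**The case against.** The best defence is that the Note already supplies the missing level. It is general and exempts nothing, so a scorer can give 2 points for full compliance and divide by 26. Equally, a scorer who follows the rows throughout divides by 25. Either way complete delivery gives 1.0. This stands, and it rules out a stronger conclusion that a reader might draw: that a patient given the whole bundle can never reach a ratio of 1. For a promptly admitted patient that happens only if the row's cap is combined with the Note's total, or if full compliance is entered as 0. The second is hard to justify, since 0 is reserved for not following the measure. The defence does not remove the contradiction, because the protocol does not say which of the two governs.

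A reader might also compute ratios of 23/26 = 0.885 or 22/26 = 0.846 for late arrivals. Both take 0 on the oxygen item with the row's cap or worse on haemoglobin, all over the Note's total. The Note allows 1 point for partial implementation or lack of time, and the oxygen item has further parts (continuation by oxygen status, saturation targets) that remain deliverable after 12 hours. These are worst-case readings and not what the protocol fixes.

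A third inference is that the scoring narrows the contrast between groups. Both issues apply to both groups, and the shift depends on a difference in full compliance that is unknown and may be near zero. No narrowing is shown.

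Finally, the haemoglobin row comes just after a break in the table, and a lost 2-point phrase in the text as read from the PDF cannot be wholly excluded. The neighbouring cells are intact, so this is unlikely, but the row should be checked against the signed protocol.

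**Conclusion.** The point holds as an internal contradiction in Appendix 1. The postoperative haemoglobin row lacks the full-compliance level that the Note and the other 12 rows provide. Scored by the row, the item merges full and partial compliance, and the denominator of secondary outcome 5 is left at 25 or 26.

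The effect is small, about 1/26 = 0.038 of the ratio per affected patient. It is limited to secondary outcome 5, objective 2 and the compliance analysis; 6-month mortality is unaffected. The conclusion assumes that the printed row is complete.

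The oxygen timing is a secondary observation. The two preoperative items use different clocks, and no entry criterion prevents the injury-based window from closing before admission. How many patients this affects is unknown, and how they should be scored is not stated. Which time window or haemoglobin threshold is clinically right is not judged here.

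**What to change.** - In Appendix 1, reconcile the postoperative haemoglobin row with the Note by adding a 2-point full-compliance level for scoring. The threshold itself does not change.
- State the total score as 26, in the Note or beside secondary outcome 5.
- Reconcile the time anchors of the preoperative oxygen and analgesia items for scoring, and say how the oxygen item is scored when its window closed before admission.

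The first two changes are one line each. Where records already exist, entries of 1 on the haemoglobin item must be checked against source to separate full from partial compliance. The oxygen rule costs more if late arrivals are to be excluded from that item: time of injury would have to be recorded, which Table 1 does not list, and denominators would then differ between patients. A rule that keeps the item in the score for everyone and states the points for late arrivals keeps a common total, though it still needs time of injury to identify them.
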